- c. hospital admission for non-invasive ventilation or high-flow oxygen therapy=4;
- d. hospital admission for oxygen therapy (but not requiring high-flow or non-invasive ventilation) =3;
- e. hospital admission but not requiring oxygen therapy=2;
- f. discharged or having reached discharge criteria (defined as clinical recovery-ie, normalization of pyrexia, respiratory rate 94% on room air, and relief of cough, all maintained for at least 72 h) =1.

2.2.2 Secondary objectives:

1. Proportion of patients in each category according to the ordinal scale
[Time Frame: 48 hours]
2. Proportion of patients in each category according to the ordinal scale [Time Frame: 7 day]
3. Proportion of patients in each category according to the ordinal scale
[Time Frame: Day 14]
4. Proportion of patients in each category according to the ordinal scale
[Time Frame: Day 28]
5. Duration of oxygen therapy in both groups [Time Frame: Day 28]
6. Duration of hospital stay in both groups [Time Frame: Day 28]
7. Proportion of patients on mechanical ventilation at day 7 in both groups
[Time Frame: Day 7]
8. Mortality in both groups [Time Frame: Day 7]
9. Mortality in both groups [Time Frame: Day 28]

10. Duration of Intensive Care Unit stay [Time Frame: Day 28]
11. Incidence of adverse effects in both groups [Time Frame: Day 28]
12. Presence of antibodies against SARS-CoV-2 in serum after plasma administration
[Time Frame: Day 0] (IgG Titres against S1, RBD antigen, and SARS CoV2
neutralizing antibody titres)
13. Presence of antibodies against SARS-CoV-2 in serum after plasma administration
[Time Frame: Day 7] (IgG Titres against S1, RBD antigen, and SARS CoV2
neutralizing antibody titres)
14. Change in Cytokines in both groups
15. Change in acute phase reactants in both groups

Section 3: Study Methods

3.1 Trial design: It will be a open-labeled; phase III randomized controlled trial.

3.2 Randomization: The randomization will be done by using stratified block randomization method into two treatment groups. The allocation concealment will be done by using “Sequentially Numbered Opaque Sealed Envelopes” (SNOSE) method.

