5.3 Recruitment: Consort flow will include as per protocol-

Patients will be assessed for eligibility >>>randomization will be done for eligible participants >>> Allocation of treatment in two groups (one arm will be given convalescent plasma with standard medical treatment and another arm will be given standard medical treatment only) >>> follow up till 28 days.

5.4 Withdrawal/ Follow-up: Withdrawal is not expected, follow up till 28 days in all enrolled patient.

5.5 Baseline patient characteristics: following variables will be considered:

- Age at screening (years) = date of screening.
- Time from initial admission to randomization(days) = date of transfusion allotment by snooze method and transfusion of plasma.
- O₂ saturation at baseline.
- PiO₂/FiO₂ ratio at baseline.
- Respiratory rate at baseline.
- Need of Mechanical ventilation at baseline.
- SOFA score at baseline.
- For those who died: Date of death – transfusion start date or date of randomization.
- For those who are alive: Date of last follow-up – transfusion start date or date of randomization.

Section 6:

Analysis

6.1 Outcome definitions:

6.1.1 Definition of primary endpoint: Time to clinical improvement (Clinical improvement: Reduction of two points in ordinal scale or live discharge from the intensive care unit, whichever is earlier)

6.1.2 Secondary endpoints:

1. The proportion of patients in each category according to the ordinal scale at 48 hours and day 7, 14, and 28 after randomization
2. Duration of oxygen therapy
3. Duration of hospital stay
4. The proportion of patients on mechanical ventilation at day 7. (after randomization)
5. Mortality at day 7 and day 28 (after randomization)
6. Duration of Intensive Care Unit stay
7. Incidence of adverse effects in both groups
8. Presence of antibodies against SARS-CoV-2 in serum after plasma administration.
9. Cytokines and acute phase reactants

6.2 Analysis methods:

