Continuous variables will be expressed as mean (SD) or median (range) and compared by Student's t-test or Mann-Whitney U test as appropriate. The categorical data will be analyzed using Chi-Square or Fisher's exact test. To compare pre and post values, a paired t-test or Wilcoxon signed-rank test will be used. To find out the predictor in survival analysis Cox-proportional hazard regression analysis will be applied. The actuarial probability of survival will be calculated by the Kaplan-Meier graph and compared by the log-rank test. The p value < 0.05 will be considered statistically significant.

6.3 Missing data: Not expected, if data are, we will try to impute.

6.4 Additional analyses: Not planned, if required an appropriate analysis will be carried out.

6.5 Harms: The risks will be the same as the risks related to the transfusion of Plasma Components, which are described below in the table. No additional risks of transfusing Convalescent plasma (CP) therapy are expected as a part of enrolment in this study as per previous literature available. The patient will be managed according to the standard of care at treatment centre. All the adverse transfusion events will be recorded and managed by clinicians or investigators as per standard treatment. Risk of Transfusion transmitted Infections (TTI) like transmission of HIV, Hepatitis B and Hepatitis C, Syphilis, and Malaria are very rare due to standard TTI testing of plasma donors at ILBS, New Delhi as per Drug and Cosmetics Act and Rules.

6.6 Statistical software: All statistical tests will be performed using SPSS for Windows version 22 (SPSS IBM Corp. Ltd. Armonk, NY).

6.7 Important references:

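### The SAP gives no rule for patients who die in the three duration endpoints and Day 7 ventilation, so a mortality difference can bias them towards the arm with more early deaths

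*SAP*

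**What the plan says.** Section 6.1.2 of the SAP lists "Duration of oxygen therapy", "Duration of hospital stay" and "Duration of Intensive Care Unit stay" by name only. Section 2.2.2 adds a time frame, for example "Duration of hospital stay in both groups [Time Frame: Day 28". Section 6.1.2 also lists "The proportion of patients on mechanical ventilation at day 7", counted from randomisation.

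Section 6.2 (repeated in 3.5.4) gives tests by type of variable, not by endpoint. Continuous variables are "compared by Student's t-test or Mann-Whitney U test as appropriate". For proportions, "The categorical data will be analyzed using Chi-Square or Fisher's exact test". Kaplan-Meier, log-rank and Cox methods are named for survival only.

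Section 4.3.2 defines the population as everyone randomised and makes it the default for all summaries and analyses. Death is scored in one place, as the worst category (6) of the ordinal scale in section 2.2.1. It is reported separately as mortality at Days 7 and 28. No text says what value a patient who dies receives in the four endpoints above.

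**The concern.** Death ends oxygen therapy, hospital stay, ICU stay and ventilation. If patients who die stay in the analysis with the days they accrued, someone who dies on Day 3 has a shorter stay than a survivor discharged on Day 12. A two-sample test then reads the death as the better result. In the same way, a patient dead before Day 7 is not on a ventilator at Day 7.

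Deaths are to be expected. Section 5.2.1 enrols severe cases, including ventilated patients, and mortality is itself an endpoint. If plasma changes mortality in either direction, these four secondary comparisons can point the wrong way. Because the rule is open and the trial is open-label (section 3.1), the handling of deaths could also be chosen after the data are seen.

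**Working it through.** **Figures in the plan.** The SAP states no mortality, stay or ventilation figure for these endpoints, so there is nothing of its own to reproduce. Section 3.3 supplies only the size: 400 enrolled in equal arms, 200 per arm. Everything else below is an assumption.

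**Mean duration if stay ends at death.** Let survivors in both arms have the same mean stay S, let deaths occur at mean day D, and let mortality be m.

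Mean = (1 − m) × S + m × D, so the arms differ by (difference in m) × (S − D).

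With S = 14 and D = 7:
- 15% mortality: 0.85 × 14 + 0.15 × 7 = 12.95 days
- 30% mortality: 0.70 × 14 + 0.30 × 7 = 11.90 days
- The higher-mortality arm looks 0.15 × 7 = 1.05 days better.
- At 20% versus 30% the gap is 0.10 × 7 = 0.7 days.

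The gap is zero when D = S and changes sign when deaths come later than typical discharge.

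**How often the test is misled.** Simulation with 200 per arm, identical survivor stays (gamma, mean 14, shape 2 or 4, capped at 28), gamma death times (shape 2) and two-sided Mann-Whitney at 0.05. The table gives the share of trials that significantly favour the higher-mortality arm (nominal 2.5%), to within a percentage point or two of simulation error.

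| Mortality | Mean death Day 5–10 | Mean death Day 14 |
|---|---|---|
| 15% vs 30% | about 11–56% | near nominal (2–4%) |
| 20% vs 30% | about 6–29% | near nominal |
| 13% vs 18% | about 4–9% | near nominal |

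Within each range, the high end belongs to the earliest deaths and the narrower survivor distribution.

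A second model uses log-normal survivor stays (median 14, log-SD 0.5, capped at 28). It gives 14–34% at 20% versus 30%, and 24–62% at 15% versus 30%, for mean death on Day 10 down to Day 5. At 20% versus 30%, its mean difference is within −0.2 to +0.1 days for mean death on Day 14 to 18, and reverses to +0.3 days at Day 22.

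**Effect of scoring deaths as 0 free days.** In the gamma scenarios, false favouring of the higher-mortality arm falls to about 0–0.7%.

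**Ventilation at Day 7.** Assume 30% are ventilated or dead in both arms, with 15% versus 5% dead by Day 7. Those counted as ventilated are 30% − 15% = 15% (30/200) and 30% − 5% = 25% (50/200).
- Pooled proportion: 80/400 = 0.20
- Standard error: √(0.20 × 0.80 × 2/200) = 0.04
- z = 0.10/0.04 = 2.5, p = 0.012, in favour of the arm with more deaths

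With 10% versus 5% dead by Day 7, the split is 20% versus 25% and p = 0.23. Scored as ventilated or dead, both arms are at 30% in either case.

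**The case against.** The strongest reply is that the SAP is silent. It nowhere says that a stay ends at death or that a dead patient counts as not ventilated, and worst-value scoring or a survivors-only analysis is equally unstated. A reader might infer that the plan prescribes a test that rewards death, but the text does not support that. The reply therefore stands as to wording. It does not remove the problem. The plain intention-to-treat reading produces the bias, while a survivors-only comparison departs from section 4.3.2 and conditions on an outcome that arises after randomisation.

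Second, the plan has safeguards. The Day 7 ordinal table shows death (6) and ECMO or mechanical ventilation (5) side by side, and mortality at Days 7 and 28 is reported. A misleading ventilation result would be visible there. This limits the ventilation concern but repairs neither that test nor the durations.

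Third, the size depends on early deaths and a sizeable mortality difference. The only fatality figure in the SAP, 1.2–13% in section 2.1, is general and not specific to severe patients. This stands, and it is why a range is given.

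Fourth, a reader might also count the cut-off at Day 28 as a fault. It is not: Day 28 is the stated time frame and applies to both arms.

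**Conclusion.** The point holds as a gap in the analysis rules for four secondary endpoints. With no rule for deaths, the natural intention-to-treat analysis is biased towards the arm with more early deaths whenever mortality differs.

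The size is conditional. Under the assumptions above it runs from slightly over the nominal 2.5% (small mortality difference) to more than half of trials (doubled mortality, mean death on Day 5). It is negligible if deaths come at about the time of typical discharge. No single figure should be quoted as the trial's own error rate.

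Nothing here shows that the trial's results are wrong or which arm would benefit, and the primary endpoint is not affected. The change should be made, but the trial's main conclusion does not depend on it.

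**What to change.** In sections 6.1.2 and 6.2:

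- Compare the arms on days alive and free of oxygen, days alive and out of hospital, and days alive and out of ICU, each to Day 28, with 0 for anyone dead by Day 28, by Mann-Whitney. Time to live discharge with death as a competing event is an acceptable alternative.
- Keep the raw durations as descriptive summaries only.
- Compare the proportion on mechanical ventilation or dead at Day 7 over all randomised patients. This is categories 5 and 6 of the ordinal table already planned for that day.

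The cost is SAP wording and a few derived variables from data that the listed endpoints already require. Sample size and trial conduct do not change. The downside is that free days are a composite that mortality can drive, and they are less direct to read than length of stay. They should therefore be reported beside the planned mortality endpoints.

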3.3 Sample size: The sample size was calculated by assuming median survival in SMT as 24 days, and convalescent plasma with 18 days giving a reduction of 25% of the median time; then with $\alpha=5\%$ and $\beta=20\%$, we need to enrol 190 participants in each treatment arm by survival analysis method. $(Z_{1-\alpha/2}+z_{\beta})^2/((\ln(\theta))^2)$ where $Z_{1-\alpha/2}=1.96$ and $z_{\beta}=0.84$, $\theta=\lambda_1=\log 2/24$ $\lambda_0=\log 2/18$. Hence, we enrolled 400 cases which were equally and randomly allocated into two arms

3.3 Framework: it will be a comparative trial with the motive of testing the efficacy of convalescent plasma in severe COVID 19 patients with standard medical trial.

3.4 Treatment allocation:

Patients will be randomized to one of two groups by block randomization:

- **Group A:** Convalescent Plasma plus standard medical treatment
- **Group B:** Standard medical treatment only.

3.5 Statistical interim analysis and stopping guidance:

3.5.1 Statistical interim analysis:

Since it is of short duration trial no interim analysis is proposed.

3.5.2 Stopping guidance: No stopping rule is proposed until or unless ethical or IRB or designated government authority may ask for stopping the trial.

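### No ordered test is named for the six-level ordinal scale, so by default it falls to Chi-square or Fisher, which ignores the order and under a moderate consistent shift loses about 20 to 25 points of power

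*SAP*

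**What the plan says.** SAP 2.2.1 defines a six-point scale that is ordered by construction, from 1 (discharged or fit for discharge) to 6 (death). The first four secondary objectives in 2.2.2 compare the arms on it at 48 hours and Days 7, 14 and 28; one reads "Proportion of patients in each category according to the ordinal scale [Time Frame: 7 day". Section 6.1.2 lists the same endpoint first among the secondary endpoints: "The proportion of patients in each category according to the ordinal scale".

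The test rule in 6.2, repeated from 3.5.4, is generic: "The categorical data will be analyzed using Chi-Square or Fisher's exact test". The sentence before it gives Student's t-test or Mann-Whitney to continuous variables. The significance rule is "The p value < 0.05 will be considered statistically significant", and 4.1 promises 95% confidence intervals. Section 6.4 plans no further analyses but allows a suitable one if it proves necessary.

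The only sample-size figure belongs to the primary time-to-improvement endpoint (3.3): "we need to enrol 190 participants in each treatment arm by survival analysis method". The SAP gives no power, effect size or category distribution for the ordinal scale.

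**The concern.** A 2 x 6 Chi-square or Fisher test returns the same p-value if the six labels are shuffled, so discharge and death are interchangeable to it. With all levels occupied it spends 5 degrees of freedom asking whether the two distributions differ in any way. The trial asks whether plasma moves patients toward recovery, which is a one-direction question that a 1-df ordered test addresses. The unordered test also supplies no single measure of the shift on which to put the confidence interval that 4.1 promises.

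At stake is the reading of four secondary comparisons. A real shift could be missed more often than necessary. Because no test is tied to the scale by name, the choice could also be made after the data are seen.

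**Working it through.** **1. The plan's own figure.** SAP 3.3 is based on "assuming median survival in SMT as 24 days, and convalescent plasma with 18 days giving a reduction of 25% of the median time", with normal quantiles 1.96 and 0.84. Per arm, 2(1.96 + 0.84)² / [ln(24/18)]² = 2 × 7.84 / 0.08276 = 189.5, so 190 reproduces. (Without the factor 2, as the formula is printed, the result is 94.7.) This figure concerns the primary endpoint and says nothing about power for the ordinal scale. What carries over is 400 patients, hence 200 per arm, and a two-sided 5% level.

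**2. Analytic comparison.** A 1-df test has 80% power at two-sided 5% when the noncentrality is 7.85. With the same noncentrality spread over more degrees of freedom, the unordered test has:

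| Occupied levels | df | Power | Loss (points) |
|---|---|---|---|
| 3 | 2 | 70.9% | 9 |
| 4 | 3 | 64.5% | 15–16 |
| 5 | 4 | 59.5% | 20–21 |
| 6 | 5 | 55.5% | 24–25 |

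**3. Simulation.** 20,000 trials per cell, 200 per arm, Pearson Chi-square against the tie-corrected Wilcoxon-Mann-Whitney test, with a proportional-odds shift. The control distributions (levels 1 to 6, %) are assumptions. Entries are power in %, Chi-square / rank test.

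| Assumed control distribution | OR 1.3 | OR 1.5 | OR 1.7 | OR 2.0 | OR 2.5 |
|---|---|---|---|---|---|
| 48 h, six levels: 1/3/30/45/18/3 | 15.1 / 29.1 | 34.2 / 59.2 | 56.8 / 81.5 | 82.8 / 96.1 | 98.2 / 99.9 |
| Day 7: 8/12/30/25/15/10 | 16.1 / 30.8 | 37.0 / 62.4 | 61.1 / 84.6 | 86.9 / 97.3 | 98.7 / 99.9 |
| Day 14: 35/12/15/10/10/18 | 16.6 / 30.7 | 36.0 / 61.2 | 59.0 / 82.9 | 85.4 / 96.8 | 98.5 / 99.9 |
| Day 28: 65/4/4/3/4/20 | 12.4 / 23.3 | 25.9 / 47.7 | 42.6 / 68.3 | 66.2 / 87.9 | 89.2 / 98.2 |
| 48 h, four levels: 0/0/33/43/20/4 | 18.9 / 29.7 | 41.4 / 58.5 | 65.5 / 81.2 | 88.7 / 95.8 | 99.0 / 99.8 |
| 48 h, three levels: 0/0/35/45/20/0 | 22.0 / 28.8 | 47.0 / 57.8 | 71.1 / 80.0 | 91.5 / 95.4 | 99.4 / 99.8 |

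With six levels the loss is 11 to 15 points at OR 1.3, 22 to 26 at OR 1.5 and 1.7, 10 to 22 at OR 2.0 and 1 to 9 at OR 2.5. A further assumed distribution, 30/15/20/12/8/15, gives 37 / 62 at OR 1.5 and 71 / 90 at OR 1.8. With four levels the largest loss is 17 points, with three levels 11. At OR 1.0 both tests reject in about 4 to 5% of trials, so Chi-square is valid; it is only less sensitive to a shift.

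**4. Where the shift is not consistent.** Three assumed patterns, control against plasma:

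- Day 28, 65/4/4/3/4/20 against 65/4/8/6/7/10 (deaths halve, discharges unchanged): Chi-square 82%, rank test 10%.
- Day 14, 35/12/15/10/10/18 against 30/20/20/12/8/10 (fewer deaths but fewer discharges): 76% and 13%.
- Day 28, 65/4/4/3/4/20 against 75/4/4/3/4/10 (deaths become discharges): 58% and 70%.

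The first pattern is a genuine benefit that the ordered test would mostly miss. It is, however, a mortality difference of 20% against 10%, and 28-day mortality is a separate endpoint. A two-proportion test with 200 per arm has z = (0.10 − 1.96 × √(2 × 0.15 × 0.85/200)) / √((0.20 × 0.80 + 0.10 × 0.90)/200) = (0.1000 − 0.0700) / 0.0354 = 0.85, or about 80% power.

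**The case against.** The strongest case for leaving the plan alone has four parts.

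*The assignment is inferred.* A reader might say that the SAP tests the scale with Chi-square. It does not say so; the rule is generic. This stands as a limit on wording. But an endpoint defined as proportions in categories is categorical data, no other rule covers it, and choosing the test is the SAP's own task.

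*The size is conditional.* A reader might infer a loss of 20 to 25 points at every one of the four time points. The document does not support that, because it gives no distribution or effect size. It even points the other way at 48 hours: the discharge criteria in 2.2.1 must hold for 72 hours, entrants are severely ill, and 5.2.2 excludes patients expected to die within 24 hours. Levels 1 and 6 may then be nearly empty. This objection stands.

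*Direction is not lost.* A reader might infer that a significant Chi-square could not show which arm did better. That goes too far, because the category proportions by arm are the endpoint and would be reported. Day 7 ventilation and mortality at Days 7 and 28 are also separate, directional binary endpoints. What remains is that the unordered test gives no single effect measure with a confidence interval.

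*Chi-square fits the wording of the endpoint and can win.* It controls type I error, matches an endpoint phrased as category proportions, and is stronger in two of the three patterns in step 4. A common odds ratio is a different summary and not merely a different test. This is why the change is an improvement and not the repair of an invalid analysis. The simulations also used the unadjusted rank test; the baseline-adjusted model was not simulated.

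**Conclusion.** The point holds in conditional form. By default the SAP places an ordered six-level endpoint under an unordered test and names no ordered alternative. Under a proportional-odds shift with 200 per arm, five or six occupied levels and an odds ratio of about 1.5 to 1.8, the cost is about 20 to 25 points of power, or 56% against 80% in the 5-df analytic case. With three or four occupied levels it is about 10 to 17 points at moderate effects. It shrinks toward zero for weak or very strong effects and can reverse when the shift is not consistent. All these figures rest on assumed distributions. The endpoint is secondary, and the primary time-to-improvement conclusion does not depend on it. The change is worth making because it is cheap and settles the test in advance.

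**What to change.** In SAP 6.2, name one ordered analysis for the scale at each of 48 hours and Days 7, 14 and 28. Either of these would do:

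- a proportional-odds model with arm and baseline category, death scored 6 and all randomised patients included, reporting the common odds ratio with its 95% confidence interval; or
- the Wilcoxon-Mann-Whitney test, already in the plan, with its use extended to this scale.

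The model is preferable where an effect estimate is wanted. Keep the category proportions by arm as a descriptive table, and keep Chi-square or Fisher for binary endpoints such as ventilation at Day 7 and mortality.

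The cost is a few sentences. No extra data are needed, because the primary endpoint already requires the baseline category, and ordinal regression is available in SPSS, the package named in 6.6. The downside is that a single summary assumes a roughly consistent shift and has low power for mixed patterns. The descriptive table would show such a pattern, and the separate mortality endpoint covers the case where the effect is confined to death.

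### For the cytokine and acute-phase change endpoints the only pre/post test named is within-patient, so no baseline-adjusted comparison of the arms is fixed; the Day 0 antibody measure is also labelled as post-plasma

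*SAP*

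**What the plan says.** Section 6.2 of the SAP, repeated word for word in section 3.5.4, names two kinds of test for continuous data. The first sentence is general: "Continuous variables will be expressed as mean (SD) or median (range) and compared by Student's t-test or Mann-Whitney U test as appropriate". Later in the paragraph comes the only sentence on change over time: "To compare pre and post values, a paired t-test or Wilcoxon signed-rank test will be used". Neither sentence is assigned to a named endpoint.

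The endpoints concerned are in section 2.2.2. Objective 14 is "Change in Cytokines in both groups" and objective 15 is "Change in acute phase reactants in both groups". Section 6.1.2 lists the same two sets of markers without the word change.

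Objectives 12 and 13 share one description, "Presence of antibodies against SARS-CoV-2 in serum after plasma administration", with IgG and neutralising titres at Day 0 (objective 12) and Day 7 (objective 13). Section 6.1.2 repeats the description without a day. Under section 3.4, Group B receives "Standard medical treatment only". The Framework paragraph of section 3 describes the trial as comparative.

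**The concern.** The question for objectives 14 and 15 is whether plasma alters the course of these markers. In an acute illness they can move in both arms whatever the treatment, through recovery, deterioration or regression to the mean. A paired test within an arm picks up that movement. It gives no estimate of the difference between arms and no confidence interval for it.

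Two things follow. First, an analyst who reaches for the method attached to pre and post values will have two within-arm p-values and may be drawn to contrast them. Second, an analyst who uses the two-sample tests instead must decide, possibly after seeing the data, whether to test the post value or the change score. Neither choice makes good use of the baseline.

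The antibody wording is a separate problem. Read literally, a Day 0 titre taken after plasma includes transfused antibody in Group A, and in Group B the description refers to an event that does not happen. Anyone who later takes Day 0 as a baseline needs to know which side of the transfusion the sample lies on.

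**Working it through.** The SAP gives no sample size, SD or correlation for these endpoints, so there is no stated figure to reproduce. The inputs are 200 patients per arm (400 allocated equally, section 3.3) and a 0.05 significance level (sections 4.1 and 6.2). Within-arm power, the size of the common change and the pre-post correlation are assumptions, shown over a range.

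**Step 1: what contrasting two paired tests would do.** Suppose both arms have the same true change, and each arm's paired test has power p. The arms are independent, so:

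P(exactly one arm significant) = p(1-p) + (1-p)p = 2p(1-p)

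| Within-arm power p (assumed) | 2p(1-p) |
|---|---|
| 0.50 | 2 × 0.50 × 0.50 = 50% |
| 0.80 | 2 × 0.80 × 0.20 = 32% |
| 0.99 | 2 × 0.99 × 0.01 = about 2% |

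In half of these trials the significant arm is plasma: 25%, 16% and about 1%.

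**Step 2: check by simulation.** This used 20,000 trials with 200 per arm, normal change scores and no true difference between arms. The common change is in units of the SD of change.

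| Common change (SD) | Exactly one arm significant | Plasma significant, control not | Between-arm t-test on change significant |
|---|---|---|---|
| 0 | 9.5% | 4.8% | 5.2% |
| 0.14 | 51% | 26% | 5.1% |
| 0.20 | 31% | 15% | 5.0% |

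Changes of 0.14 and 0.20 SD correspond to within-arm power of about 0.5 and 0.8, so the simulation agrees with the formula. A larger common change takes the figure down again. At 0.3 SD the standardised mean is 0.3 × √200 = 4.24, power is about 0.99, and 2p(1-p) is about 2%.

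**Step 3: what baseline adjustment gains.** Let the marker, on the log scale, have variance σ² before and after, with correlation r. Per patient, the variance that enters the arm comparison is:

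- post value alone: σ²
- change score: 2σ²(1-r)
- ANCOVA: σ²(1-r²)

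ANCOVA relative to the change score is (1-r²) / [2(1-r)] = (1+r)/2. Relative to the post value alone it is 1-r².

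| r (assumed) | ANCOVA / change score | ANCOVA / post value |
|---|---|---|
| 0.3 | 1.3/2 = 0.65 | 1 - 0.09 = 0.91 |
| 0.5 | 1.5/2 = 0.75 | 1 - 0.25 = 0.75 |

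Both ratios are below 1 for any r strictly between 0 and 1, so ANCOVA does better than either unadjusted two-sample test that section 6.2 would allow.

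**Step 4: the Day 0 label.** No arithmetic applies. Objective 12 places the measure at Day 0 and describes it as following plasma; section 3.4 gives Group B no plasma; section 6.1.2 keeps the description and drops the day. Section 5.5 does not settle the matter: its baseline list has no antibody value, and for follow-up it counts from either the start of transfusion or the date of randomisation. On the SAP's text, the Day 0 sample cannot be placed before or after transfusion with confidence.

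**The case against.** The strongest reply is that the SAP does provide for comparing the arms. The first sentence of section 6.2 names two-sample tests for continuous variables, the trial is declared comparative, and section 6.1.2 lists the markers without the word change. A change score is itself a continuous variable, and nothing says the paired tests replace the between-arm tests. This stands. A reader might infer that the arms are not compared at all on these endpoints; the SAP does not say that. What remains is that neither test is assigned to objectives 14 and 15, and the only one attached to pre and post values is within-patient.

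Nor does the SAP say that significance in one arm but not the other will be read as a treatment effect. That also stands. The percentages in steps 1 and 2 describe a possible misuse, not the error rate of a stated analysis, and they become small when the common change is large.

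On antibodies, a reader might infer that titres are to be tested by paired tests from a contaminated baseline. The documents do not support this. Objectives 12 and 13 concern presence and titre at two days, not change, and nowhere is Day 0 called the pre value. One phrase serves both days, so Day 0 may be a pre-transfusion sample with the wrong label, and sampling schedules are commonly left to the protocol. The defect is in the label and does not show that the sample was wrongly timed.

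The background's idea that plasma helps before a humoral response is rationale only. No objective tests it, so it adds nothing to the point.

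**Conclusion.** The point holds in a limited form. For objectives 14 and 15 the SAP fixes no baseline-adjusted comparison of the arms, and the only method it ties to pre and post values does not estimate a treatment effect. If within-arm p-values were contrasted, discordant results with no arm difference would occur in anything from about 2% to 50% of trials, depending on the assumed within-arm power; a direct between-arm test on change stays near 5%. ANCOVA reduces the variance by 25% against either unadjusted test at r = 0.5, and by 35% (change score) or 9% (post value) at r = 0.3. These ratios assume equal variance before and after and a common linear slope; r is not given in the SAP.

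The Day 0 label in objective 12 is a real wording defect: it is undefined for controls and, read literally, is not a pre-treatment value in the plasma arm. Whether the sample itself is affected cannot be decided from the SAP.

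The primary endpoint and the clinical secondary endpoints are untouched. The change is worth making because it costs little.

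**What to change.** 1. In section 6.2, assign objectives 14 and 15 to a between-arm ANCOVA: log post value on arm and log baseline value, at a named post time point. Report the ratio of geometric means with its 95% confidence interval. Keep paired t-tests and signed-rank tests as descriptive summaries within arms, and state that they are not used to compare arms.

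2. Reconcile the wording of objective 12 with when the Day 0 blood is actually drawn.
   - If it is drawn before transfusion, and at randomisation in controls, call it baseline and use it as the covariate for the Day 7 titre (objective 13). The ANCOVA does not apply to objective 12, which is then the baseline itself.
   - If it is drawn after transfusion, keep the label for Group A, define the matching time for Group B, and do not use the value as a baseline.

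The cost is a few lines of SAP text and a little more analysis work. Item 1 needs no new samples, because a change endpoint already requires a pre value. For antibodies, a usable baseline exists only if the Day 0 sample precedes transfusion.
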